Wear and Replacement Schedules	Wear Schedule: Daily Disposable Replacement Schedule: Daily Disposable
Objectives	The primary objective of this study is to gain clinical insights of the study lenses and solutions with respect to comfort.
Study Endpoints	Primary endpoint: subjective assessment of initial comfort using Visual Analog Scale (VAS) Other Endpoints: Expanded corneal staining, ocular physiology, subject's reported ocular symptoms, and ocular adverse events.
Study Design	This is a multi-site, randomized, double-masked, contralateral, 2 treatment x 2 period crossover, dispensing, five-visit study. See the flow chart at the end of the synopsis table for the schematic of the study visits and procedures of main observations (Figure 1).
Sample Size	Up to 120 subjects are targeted to be enrolled and approximately 90 subjects are targeted to complete the study.
Study Duration	The study will last approximately 4 months and include a 2-month enrollment period.

Anticipated Study Population	Up to 120 healthy subjects ages 18-69 years that are current soft contact lens wearers will be recruited for this clinical study.
Eligibility Criteria	
Potential subjects must satisfy all of the following criteria to be enrolled in the study:
 
 1. Subjects must be 18-69 years of age (inclusive) 2. Subjects must be habitual disposable hydrogel or silicone hydrogel (1-day, 2-week, or monthly replacement schedule) soft lens wearer in both eyes. Habitual is defined as at least one (1) month of contact lens wear where the lenses are worn for a minimum of six (6) hours per day and a minimum of five (5) days per week 3. Subjects must have best corrected visual acuity of 20/25 (Snellen or equivalent) or better in each eye 4. The subject's refractive sphere (vertexed) must be between -1.00 and -6.00 D in each eye. 5. The subject's refractive cylinder must be less than or equal to -1.00 D in each eye 6. The subject must have normal eyes (i.e., no ocular medications or infections of any type) 7. Subjects must possess a functional/usable pair of spectacles and bring them to the visit (only if applicable - to the investigators discretion) 8. Subjects must read, understand, and sign the Statement of Informed Consent 9. Subjects must appear able and willing to adhere to the instructions set forth in this clinical protocol. 
Potential subjects who meet any of the following criteria will be excluded from participating in the study:
 
 1. Currently pregnant or breast-feeding 2. Diabetes 3. Any ocular or systemic allergies or disease which may interfere with contact lens wear (at the discretion of the investigator) 4. Any systemic disease, autoimmune disease, or use of medication which may interfere with contact lens wear (at the discretion of the investigator) 5. Any infectious diseases (e.g. hepatitis, tuberculosis) or a contagious immunosuppressive disease (eg, HIV), by self-report 6. Current habitual use of Restasis, Xiidra, ocular steroids, or any medication (RX or OTC) that may interfere with contact lens wear (at the discretion of the investigator) 7. Grade 2 or greater corneal staining or conjunctival injection on the FDA scale

	
 8. Clinically significant (Grade 3 or greater on the FDA scale) corneal edema, corneal vascularization, or any other abnormalities of the cornea (excluding corneal staining) which would contraindicate contact lens wear 9. Clinically significant (Grade 3 or greater on the FDA scale) tarsal abnormalities which might interfere with contact lens wear 10. Any active ocular abnormalities/conditions that may interfere with contact lens wear (at the discretion of the investigator) 11. Any corneal distortion due to previous rigid gas permeable lens wear, surgery or pathology 12. History of any ocular or corneal surgery (eg, RK, PRK, LASIK) 13. Habitual contact lens wear modality as extended wear 14. Participation in any pharmaceutical or medical device related clinical trial within 7 days prior to study enrollment 15. History of binocular vision abnormality or strabismus 16. Habitual wearers of rigid gas permeable lens within the past 3 months 17. Employees of investigational clinic (investigator, coordinator, and technician etc.) or family members of employees of the investigational clinic by self-report.
Disallowed Medications/Interventions	Current habitual use of Restasis, Xiidra, ocular steroids, or any medication (RX or OTC) that may interfere with contact lens wear (at the discretion of the investigator)
Measurements and Procedures	Safety parameters (slit lamp findings, adverse events), subject reported symptoms, comfort rating (VAS) and lens fit.
Microbiology or Other Laboratory Testing	None
Study Termination	The occurrence of one or more Unanticipated Adverse Device Effect (UADE), or any SAE where relationship to study agent cannot be ruled out, will result in stopping further dispensing investigational product. In the event of a UADE or SAE, the Sponsor Medical Monitor may unmask the treatment regimen of subject(s) and may discuss this with the Principal Investigator before any further subjects are enrolled.
Ancillary Supplies/ Study-Specific Materials	Laci-pure, EyeCept re-wetting drops, Opti-Free, ClearCare, slit lamp, Snellen VA chart, fluorescein, auto-refractors, phoropters
Principal Investigator(s) and Study Institution(s)/Site(s)	A full list of Principal Investigators, clinical sites, and institutions is kept separately from the Study Protocol and is included in the study Trial Master File.

Figure 1: Study Flowchart

COMMONLY USED ABBREVIATIONS AND DEFINITIONS OF TERMS

ADD	Plus Power Required for Near Use
ADE	Adverse Device Effect
AE	Adverse Event/Adverse Experience
BCVA	Best Corrected Visual Acuity
BSCVA	Best Spectacle Corrected Visual Acuity
CFR	Code of Federal Regulations
CLUE	Contact Lens User Experience
COAS	Complete Ophthalmic Analysis System
COM	Clinical Operations Manager
CRA	Clinical Research Associate
CRF	Case Report Form
CRO	Contract Research Organization
CT	Center Thickness
CTP	Clinical Technical Procedure
D	Diopter
DMC	Data Monitoring Committee
eCRF	Electronic Case Report Form
EDC	Electronic Data Capture
ETDRS	Early Treatment Diabetic Retinopathy Study
FDA	Food and Drug Administration
GCP	Good Clinical Practice
HIPAA	Health Insurance Portability and Accountability Act
IB	Investigator's Brochure
ICF	Informed Consent Form
ICH	International Council for Harmonization
IDE	Investigational Device Exemption
IEC	Independent Ethics Committee
IRB	Institutional Review Board
ISO	International Organization for Standardization
ITT	Intent-to-Treat
JJVC	Johnson & Johnson Vision Care, Inc.
LC	Limbus Center
LogMAR	Logarithm of Minimal Angle of Resolution
MedDRA [®]	Medical Dictionary for Regulatory Activities
MOP	Manual of Procedures
NIH	National Institutes of Health
OD	Right Eye
OHRP	Office for Human Research Protections
OHSR	Office for Human Subjects Research
OS	Left Eye
OU	Both Eyes
PD	Protocol Deviation
PHI	Protected Health Information
PI	Principal Investigator
PIG	Patient Instruction Guide

PQC	Product Quality Complaint
PRO	Patient Reported Outcome
QA	Quality Assurance
QC	Quality Control
SAE	Serious Adverse Event/Serious Adverse Experience
SAP	Statistical Analysis Plan
SAS	Statistical Analysis System
SD	Standard Deviation
SOP	Standard Operating Procedure
UADE	Unanticipated Adverse Device Effect
USADE	Unanticipated Serious Adverse Device Effect
VA	Visual Acuity

1. INTRODUCTION AND BACKGROUND

Reusable soft contact lenses require regular cleaning and disinfection to prevent lens deposits and infections. Multi-purpose care solution is the most commonly used lens care system. They are designed to rinse, disinfect, clean, and store soft lenses. The purpose of this study is to evaluate the subjective comfort of 3 ACUVUE® brand contact lenses with 2 multi-purpose solutions (Test and Control) and one peroxide solution (Control) when lenses are worn for 45 minutes and 2 hours.

1.1. Name and Descriptions of Investigational Products

The investigational products in this study are 3 lens care solutions: RevitaLens® Multi-Purpose Disinfecting Solution (Test), CLEAR CARE® Contact Lens Solution (Control 1), and OPTI-FREE® Puremoist® Multi-Purpose Contact Lens Solution (Control 2). Their evaluation will be performed on 3 reusable soft contact lenses: ACUVUE® 2, ACUVUE® OASYS®, ACUVUE Vita using a crossover design. The 1-DAY ACUVUE MOIST, a daily disposable lens, will be worn during the washout period between solution use including habitual lens care solution at baseline.

All contact lens and lens care solutions used in this study are FDA approved and marketed products.

1.2. Intended Use of Investigational Products

The proposed use of the contact lens care products is to clean and disinfect contact lenses as indicated on-label.

1.3. Summary of Findings from Nonclinical Studies

Not Applicable - Marketed products only.

1.4. Summary of Known Risks and Benefits to Human Subjects

The following risks/adverse events can be associated with wearing soft contact lenses in general:

- There may be less comfort than when the lens was first placed on the eye.
- The eyes may burn, sting and/or itch.
- There may be a feeling of something in the eye (foreign body, scratched area).
- There may be the potential for some temporary impairment due to peripheral infiltrates, peripheral corneal ulcers and corneal erosion.
- There may be the potential for other physiological observations, such as local or generalized edema, corneal neovascularization, corneal staining, injection, tarsal abnormalities, iritis and conjunctivitis, some of which are clinically acceptable in low amounts.
- There may be excessive watering, unusual eye secretions, or redness of the eye.
- Poor visual acuity, blurred vision, rainbows or halos around objects, photo-phobia, or dry eyes may also occur if the lenses are worn continuously or for too long a time.

There is no direct benefit to the subject for participating in the study, although they will be able to try out contact lenses and contact lens care products. The information from this study will aid in the further development and design of new contact lenses.

For the most comprehensive clinical information regarding the contact lenses and care products refer to the package inserts (Appendix C).

1.5. Relevant Literature References and Prior Clinical Data Relevant to Proposed Clinical Study

All lenses and care products are FDA approved and marketed products. Refer to package inserts (Appendix C) for additional information.

2. STUDY OBJECTIVES, ENDPOINTS AND HYPOTHESES

2.1. Objectives

The primary objective of this study is subjective assessment of initial comfort of 3 reusable ACUVUE Brand Contact Lenses (ACUVUE® 2, ACUVUE® OASYS®, ACUVUE Vita soaked) soaked in the 3 study lens care solutions (Test: RevitaLens®, Control 1: CLEAR CARE®, and Control 2: OPTI-FREE® Puremoist®) for 16-28 hours each. Initial comfort will be assessed at 1-min, 5-min, 45-min and 2 hours of lens wear.

2.2. Endpoints

Primary Endpoint(s):

Subjective assessment of initial comfort will be conducted using Visual Analogue Scale (VAS) of comfort. VAS of comfort consists of a vertical line which represents continuous scale from 0 (extremely uncomfortable) to 100 (extremely comfortable). VAS comfort will be administered at 1-min, 5-min, 45-min and 2-hours post-fit.

Other Endpoints:

- Expanded corneal staining [REDACTED]
- Slit-Lamp findings [REDACTED]
- Subject's reported ocular symptoms [REDACTED]
- Lens fitting assessment [REDACTED]
- Lens deposit characteristics [REDACTED]
- Lens wettability characteristics [REDACTED]
- Adverse events

2.3. Hypotheses

The test solution will be similar to the control solutions with respect to initial comfort at 1-min, 5-min, 45-min and 2 hours post-fit of pre-soaked lenses.

This is a pilot study and all the hypothesis are exploratory in nature.

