5. TEST ARTICLE ALLOCATION AND MASKING

5.1. Test Article Allocation

Subjects, in blocks of three, will be first randomly assigned to one of the three study lens types to wear throughout the study (ACUVUE 2, ACUVUE OASYS, ACUVUE Vita). Within each study lens, a contralateral 2-treatment x 2-period crossover design will be used to randomly assign subjects to wear 2 pair of lenses soaked in control solutions (CLEAR CARE and Opti-Free) and test solution (RevitaLens). Subjects in block of two will be randomized to one of the following sequences:

Sequence	Period 1	Period 2
Sequence 1	OPTI-FREE - RevitaLens	CLEAR CARE – RevitaLens
Sequence 2	CLEAR CARE – RevitaLens	OPTI-FREE - RevitaLens

At each period, subjects will be exposed to a control solution (OPTI-FREE or CLEAR CARE) in one eye and to a test solution (RevitaLens) in the contralateral eye for 2 hours using pre-soaked contact lenses. The test and control solutions will be randomly assigned to left and right eyes. A washout period will be incorporated between lens wear periods where subjects will be wearing 1-Day ACUVUE Moist, a daily disposable lens, for 5 to 7 days.

The randomization will be stratified by site and each site will receive separate randomization scheme. The study site will follow the randomization scheme provided and will complete enrollment according to the randomization list and will not pre-select or assign subjects. The assignment of the subjects must be performed at the first baseline visit (Visit 1). The following must have occurred prior to randomization:

- Informed consent has been obtained
- Subject meets all the inclusion / exclusion criteria
- Subject history and baseline information has been collected

The randomization scheme will be generated using the PROC PLAN procedure from the SAS Software Version 9.4 or higher (SAS Institute, Cary, NC).

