14.2. Sample Size Justification

This is a pilot study and the sample size was not based on any empirical power calculation. The collected data will be used to design future clinical evaluation.

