14.5. Primary Analysis

Initial comfort scores at 1-min, 5-min, 45-min and 2-hour post-fit will be analyzed using a multivariate hierarchical Bayesian model for repeated measures to test for the difference between the test solution and control solutions at 1-min, 5-min, 45-min and 120-min. The regression model will include sequence, period, solution, lens and lens by solution interaction as fixed effects. Investigational site, subjects and eye nested within subjects will be included as random effect factors.

The Model:

Let $\mathbf{y}_{ijk} = (y_{1ijk}, y_{2ijk}, y_{3ijk}, y_{4ijk})$ denote the initial comfort scores for the i^{th} eye of the j^{th} subject, from k^{th} site at 1-min, 5-min, 45-min and 2-hour post fit. The likelihood of \mathbf{y}_{ijk} is constructed as follow:

$$\mathbf{y}_{ijk} \sim N(\boldsymbol{\mu}, \boldsymbol{\Sigma}),$$

where $\boldsymbol{\mu} = (\mu_1, \mu_2, \mu_3, \mu_4)^T$ and $\boldsymbol{\Sigma}$ is a 4×4 variance-covariance matrix. Here μ_1, μ_2, μ_3 and μ_4 are given by:

$$\mu_i = \mu_0 + \beta_1 \text{sequence} + \beta_2 \text{period} + \beta_3 \text{lens} + \beta_4 \text{solution} + \beta_5 \text{lens*solution} + \delta_{i(jk)} + \delta_{j(k)} + \delta_k,$$

where $\delta_{i(jk)} \sim N(0, \sigma_{\text{eye}}^2)$, $\delta_{j(k)} \sim N(0, \sigma_{\text{subj}}^2)$, $\delta_k \sim N(0, \sigma_{\text{site}}^2)$. Other baseline characteristics such as age, gender and CLDEQ-8 score will also be included as fixed effects when appropriate.

Non-informative prior distributions will be used for the coefficients in the models as well as for the error terms: Independent vague normal $N(0, 1000)$ priors for the regression coefficients (μ_0 and $\boldsymbol{\beta}$), inverse gamma $IG(0.001, 0.001)$ for $\sigma_{\text{eye}}^2, \sigma_{\text{subj}}^2, \sigma_{\text{site}}^2$ and inverse Wishart $IW(R, 4)$ for $\boldsymbol{\Sigma}$. R is determined by $S = E[\boldsymbol{\Sigma}] = 4R$ where S is the sample variance-covariance matrix of the \mathbf{y}_{ijk} . The Metropolis sampler algorithm as implemented in the MCMC Procedure (SAS 9.4, SAS Institute, Cary, NC) will be used to estimate the posterior distributions of the unknown parameters. Inferences will be made based on a posterior credible interval for the relevant parameters. Results will be reported as regression coefficient mean estimates with 95% credible intervals.

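### Section 2.3 hypothesises similarity without defining it, section 14.5 tests for a difference, and the 14.5 equation as printed gives no solution effect by time point

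*Combined protocol and SAP*

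**What the plan says.** Section 2.3 gives the hypothesis, "The test solution will be similar to the control solutions with respect to initial comfort", at 1, 5, 45 and 120 minutes after fitting. It then qualifies it: "This is a pilot study and all the hypothesis are exploratory in nature". The objective in section 2.1 is worded as an assessment: "The primary objective of this study is subjective assessment of initial comfort".

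Section 14.5 fits a multivariate hierarchical Bayesian model "to test for the difference between the test solution and control solutions" at the same four times. On the fixed effects it says: "The regression model will include sequence, period, solution, lens and lens by solution interaction as fixed effects". The response is a vector of four scores per eye. The equation printed for its mean has an intercept and coefficients for sequence, period, lens, solution and lens by solution, none of them indexed by time. The letter i stands for the eye in the response and for the component of the mean vector in the equation. On output: "Results will be reported as regression coefficient mean estimates with 95% credible intervals".

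Sections 14.1 to 14.10 contain no VAS margin, no definition of similar, no posterior probability threshold and no rule for reading the interval. Section 14.4 sets an overall type I error rate of 5%, and section 14.6 plans no secondary analysis. Section 14.2 says the sample size has no power basis and adds: "The collected data will be used to design future clinical evaluation".

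**The concern.** There are two separate gaps.

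The first is between hypothesis and analysis. A test for a difference can count against similarity, but failing to find a difference does not establish it. With no margin, no planned result is designated as support for 2.3. An imprecise interval that includes 0, set beside the 2.3 wording, could be described as similarity and carried into the next design.

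The second is in the model. Section 2.3 and the first sentence of 14.5 both need a test-versus-control difference at each of four times. The declared output is regression coefficients, and the printed equation has no coefficient that varies with time. Programmed literally, it would return one solution effect per control (with its lens interaction) for all four times, and it would also hold mean comfort constant over time.

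**Working it through.** **No planned figure to reproduce.** The plan states no margin, expected difference, SD or power. Only the targets in section 4.3 can be checked: 3 × 30 = 90 completers, 3 × 36 = 108 randomised and 3 × 40 = 120 enrolled, all consistent.

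**How often would an interval include 0 despite a real deficit?** Inputs from the documents: about 90 completers, 30 per lens (section 4.3); a VAS from 0 to 100 (section 2.2); a 95% interval (section 14.5), taken here as two-sided. Assumptions, not in the documents: a true difference of 5 points, a paired-difference SD of 10 to 25, a normal approximation, and one paired difference per subject and control.

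SE = SD/√n, and P(interval includes 0) = Φ(1.96 − 5/SE) − Φ(−1.96 − 5/SE).

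- SD 10, n = 90: SE = 10/√90 = 1.054; 5/SE = 4.74; P = Φ(−2.78) = 0.003.
- SD 25, n = 90: SE = 25/√90 = 2.635; 5/SE = 1.90; P = Φ(0.06) = 0.52.

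| SD | n = 90: half-width | n = 90: P | n = 30: half-width | n = 30: P |
|---|---|---|---|---|
| 10 | 2.07 | 0.003 | 3.58 | 0.22 |
| 15 | 3.10 | 0.11 | 5.37 | 0.55 |
| 20 | 4.13 | 0.34 | 7.16 | 0.72 |
| 25 | 5.16 | 0.52 | 8.95 | 0.81 |

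The design may do better than one pair per control. Section 5.1 says: "At each period, subjects will be exposed to a control solution (OPTI-FREE or CLEAR CARE) in one eye and to a test solution (RevitaLens"), so the test solution is worn in both periods. With independent residuals and no eye variance, the test mean over two periods minus one control score has variance 1/2 + 1 = 1.5 residual variances, against 2 for a single pair. The SE falls by √(1.5/2) = 0.866, and the pooled range becomes under 0.001 to 0.41. The n = 30 columns are descriptive, because 2.3 states no per-lens hypothesis.

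**What does the printed equation estimate?** Take one lens, one period and two solutions with identical assumed mean comfort of 80, 83, 86 and 89 at the four times. The true solution difference is 0 at every time. Generalised least squares with subject and eye effects gives:

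- As printed (common intercept, one solution effect): a single difference of 0 and one mean of 84.5 for all times. There are no time-point estimates.
- Solution effect indexed by time, intercept not: the reference solution is held at (80 + 83 + 86 + 89)/4 = 84.5. The apparent differences are 80 − 84.5 = −4.5, 83 − 84.5 = −1.5, 86 − 84.5 = +1.5 and 89 − 84.5 = +4.5. They did not change as the residual correlation was varied from 0 to 0.6.
- Intercept and solution both indexed by time: 0 at every time, which is correct.

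The same argument applies to lens. If lens is constant over time while lens by solution is not, any change over time in the lens differences falls into the interaction.

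**Size of the corrected model.** In reference coding the fixed effects are intercept 1, sequence 1, period 1, lens 2, solution 2 and lens by solution 4, or 11 in all. Making all of them time-specific gives 4 × 11 = 44, before any baseline covariates. The solution and lens-by-solution terms go from 6 to 24.

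**The case against.** The strongest reply is that this is a pilot. Its hypotheses are declared exploratory, its objective is to assess comfort and not to demonstrate similarity, and it already reports estimates with 95% credible intervals, which is close to what an estimation aim needs. That stands, and it limits the first gap to wording and interpretation.

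A reader might infer that the plan treats an interval including 0 as proof of similarity, or that the study fails a confirmatory test. The documents support neither. No section adopts such a rule, and no confirmatory claim is made. A reader might also take the probabilities above as error rates of the plan. They rest on an assumed SD and true difference, run from negligible to large, and describe a reading that the plan does not prescribe.

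On the model, it is fair to say that the intent is clear. The text asks for differences at each time and the mean vector has four components, so the equation may be shorthand. But the equation is the specification to be programmed and its coefficients are the declared output. Adding an index to the solution terms alone, which looks like the obvious repair, gives false differences.

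**Conclusion.** Both gaps are confirmed from the text. The mismatch between 2.3 and 14.5 is modest. It affects how the pilot is described and carried forward, not its safety or conduct. Its size cannot be fixed from the documents: for an assumed 5-point deficit and SD of 10 to 25, the pooled interval would include 0 with probability about 0.003 to 0.52, or less if the design is used more efficiently.

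The missing time index rests on no assumed SD or effect. As printed, the equation cannot give the time-point differences that 2.3 and the first sentence of 14.5 call for. The 80-to-89 example uses assumed means, but its lesson does not depend on them: whenever comfort changes over time, time-specific solution terms need a time-specific intercept. Both points should be corrected before unmasking.

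**What to change.** (a) Reword 2.3 as estimation of the test-minus-control VAS difference, with its 95% credible interval, for each control and time point. State in 14.5 that an interval including 0 is not evidence of similarity. If the sponsor keeps the word similar, set and justify a VAS margin before unmasking and report the posterior probability that the difference lies within it.

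(b) In the 14.5 equation, make every fixed effect time-specific: intercept, sequence, period, lens, solution and lens by solution. At minimum, index the intercept and lens together with the solution terms. Use a different letter for time than for eye.

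**Cost.** A few sentences and a model edit, with no change to design, visits, sample size or data. The MCMC run has more parameters (11 to 44 fixed effects under full indexing), and a null result can no longer be called similarity. The margin option costs more, since the margin must be justified and a demanding rule may be out of reach. For example, if the rule required the 95% interval to lie within an assumed ±5 points, with one pair per subject and control, it could not be met once the SD exceeds 5 × √90/1.96 = 24.2 pooled, or 5 × √30/1.96 = 14.0 within one lens.
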